**Sample size calculation**

The data will be gathered from Migoli village, Mtera ward and Izazi Village, in Izazi ward (both in Iringa, population 10.036 and 2.567 people), in addition to the control villages, Kimande village in Pawaga ward and Idodi village in Idodi ward, also in Iringa district. After internal discussion in the DigI group, it is assumed that the people would have 21 correct answers out of 42 questions in total, if they were

Sample size per village			
	Population	Proportion	Sample
Migoli	10036	0,79	195
Control village 1, Kimande	3000	0,55	135
Izazi	2657	0,21	52
Control village 2, Idodi	2500	0,45	112
N	18193		
Sample			494

Table 2

asked questions from the questionnaire today. It is further assumed that the intervention will increase the number of correct answers to at least 28 of 42. The sample size calculation is to be found in appendix 1. The power of the study was set to 80%, the drop-outs calculated to be 20% and the cluster correlation was set to 1,5. After calculating the sample size, the proportions to each village was allocated, see table 2.

After ethical approval from NIMR is granted, the questionnaire will be piloted in a village near Morogoro to see how it corresponds with the assumed proportion mentioned (at least 21 correct answers out of 42).

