## **WP 2 –A cluster non-randomised controlled trial**

The overall strategy chosen is a non-randomised controlled trial, with a two-stage cluster sampling. The study will be conducted in four villages in Iringa district in Tanzania, assessing the effect of digital health messages related to HIV / AIDS, Tuberculosis (TB) and *Taenia solium* cysticercosis/taeniosis (TSCT).

The aim of the digital health intervention is to contribute to increased health knowledge of the clients that has the potential to facilitate better use of health care services, and to promote early treatment, thus to strengthen the health system.

Hypotheses: We hypothesize that the intervention increases the proportion of correct answers, related to the intervention diseases, when comparing pre and post knowledge scores, also among clients that cannot read.

We will measure if the intervention leads to an increase in the number of correctly answered questions, from 21 out of 42, to 28 out of 42 (equivalent to 16,7 % increase) questions from the study questionnaire, during the 12-months intervention in the intervention group compared to the control group.

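### At the planned 20% drop-out, 494 participants give about 79% power for 21/42 versus 28/42, slightly below the stated 80%; the likeliest cause, unconfirmed, is that 20% was added rather than divided out

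*Combined protocol and SAP*

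**What the plan says.** The design inputs are in the Sample size calculation section. For the starting level, "it is assumed that the people would have 21 correct answers out of 42 questions in total". For the effect, "the intervention will increase the number of correct answers to at least 28 of 42". The WP 2 section gives the same change as "from 21 out of 42, to 28 out of 42 (equivalent to 16,7 % increase". On power: "The power of the study was set to 80"%. On attrition and clustering: "the drop-outs calculated to be 20% and the cluster correlation was set to 1,5".

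Table 2 gives a total of 494. The intervention villages contribute 195 + 52 = 247 and the control villages 135 + 112 = 247, so allocation is in effect 1:1.

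The section does not give the significance level, the test formula, the rounding, or how the 20% was turned into extra participants. It refers elsewhere for these: "The sample size calculation is to be found in appendix 1". That appendix is not in the text available, so its absence here is not a fault in the plan.

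**The concern.** A drop-out allowance should leave the required number of completers after the losses have happened. If a fraction d is expected to leave, the completer requirement is divided by 1 - d. Multiplying by 1 + d gives a smaller number, and the shortfall appears only if losses reach the planned level.

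The total of 494 is what results from adding 20% to a standard two-proportion calculation on the plan's own inputs. Whatever its origin, 494 can be tested directly: take away 20% and see whether 80% power remains for the stated effect.

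The 20% is the only attrition allowance in the text. Intervention participants are questioned five times over 12 months, and the main outcome in Methods and study design includes how well knowledge is kept over the year. The last round, where losses will be largest, therefore bears on the main outcome.

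**Working it through.** **Inputs**

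- p1 = 21/42 = 0.5 and p2 = 28/42 = 0.6667, difference 0.1667 (Sample size calculation; WP 2 section).
- Power 80%, drop-out 20% (Sample size calculation).
- 1.5 is taken as a design effect. The plan calls it a correlation, but a correlation cannot exceed 1. This is an assumption.
- Two-sided 5% test. This is an assumption, as the text gives no significance level.
- Each person counts as one binary outcome. This is also an assumption; it is the treatment that reproduces 494.

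**Step 1. Reproduce 494**

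Pooled formula, with p the mean of p1 and p2 (0.5833):

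n = [1.960 x sqrt(2p(1-p)) + 0.8416 x sqrt(p1(1-p1) + p2(1-p2))]² / (p2-p1)²

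= [1.960 x sqrt(0.4861) + 0.8416 x sqrt(0.4722)]² / 0.02778 = 136.2, rounded up to 137.

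137 x 1.5 = 205.5 completers per group. 205.5 x 1.2 = 246.6, rounded up to 247; 2 x 247 = **494**, an exact match.

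Dividing instead: 205.5/0.8 = 256.9, rounded up to 257; 2 x 257 = **514**.

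**Step 2. Other routes (two-sided 5%, no continuity correction)**

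| p2 | Formula | n per group | Total, x 1.2 | Total, / 0.8 |
|---|---|---|---|---|
| 28/42 | pooled | 137 | 494 | 514 |
| 28/42 | unpooled | 134 | 484 | 504 |
| 0.667 | pooled | 136 | 490 | 510 |
| 0.667 | unpooled | 133 | 480 | 500 |
| 0.67 | pooled | 131 | 472 | 492 |

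The last row reaches 494 by division if the intermediate figure is also rounded: 131 x 1.5 = 196.5, up to 197; 197/0.8 = 246.25, up to 247; 2 x 247 = 494.

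The x 1.2 match depends on rounding too. Rounding up at every step gives 206 x 1.2 = 247.2, so 248 and a total of 496. Rounding only at the end gives 492.

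One-sided 5% variants at 28/42 give totals between about 378 and 448, and none gives 494.

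**Step 3. Power of 494 after 20% loss, at the stated 28/42**

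This step does not depend on how 494 was reached.

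247 x 0.8 = 197.6 per group; 197.6/1.5 = 131.7 effective.

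- Pooled: z = [0.1667 x sqrt(131.7) - 1.960 x sqrt(0.4861)] / sqrt(0.4722) = 0.795, power **78.7%**.
- Unpooled: z = 0.1667 / sqrt(0.4722/131.7) - 1.960 = 0.824, power **79.5%**.

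For comparison (pooled), 494 with no loss gives 86.9%, and 514 with 20% loss gives 80.3%.

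**Step 4. What the allowance covers on the x 1.2 route**

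Completers required: 2 x 205.5 = 411. Tolerable loss: (494 - 411)/494 = 83/494 = 16.8%. A 20% loss would be about 99 people.

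**The case against.** A reader might infer from the exact match in Step 1 that the plan is shown to have added 20% where it should have divided by 0.8. The documents do not support that. The significance level, formula, rounding and inflation method are not in the text, and appendix 1 cannot be consulted. Division by 0.8 also gives exactly 494 if 28/42 is rounded to 0.67, which is the two-decimal precision Table 2 uses for its own proportions. Each route needs one particular rounding choice, so the match cannot settle which was used. This objection stands, and the cause must remain an inference. The x 1.2 route is still the likelier: it uses the proportions as stated, and the WP 2 section gives the effect as 16.7%, whereas 0.67 - 0.50 would be 17%.

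A reader might also infer that the study is underpowered and should recruit 514, or that field staff would take 99 losses as safe. Neither follows. The total is given as approximate, the 28 correct answers as a minimum, and the 21 comes from internal discussion and is to be checked in a pilot. A difference of about one point of power lies well inside that uncertainty. No section gives the field team a limit on losses.

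The objection does not remove the result of Step 3. If 0.67 was used, power at 0.67 after 20% loss is 80.3%, but at the stated 28/42 it is still 78.7% to 79.5%.

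**Conclusion.** The point holds as a small inconsistency between stated figures. With 494 participants and 20% drop-out, power for 21/42 versus 28/42 is about 79%, which is 0.5 to 1.3 points below the stated 80%. In participants, the gap is at most about 20 (514 against 494, or 4%).

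That addition of 20% was the cause is likely but unconfirmed. The statement that 494 covers only about 17% drop-out applies only if it was.

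The power figures rest on the three assumptions listed with the inputs. The two-sided test matters most: a one-sided 5% test would need only 108 per group (pooled) before inflation, so 131.7 would be ample, but such a design does not lead to 494. Severity: minor.

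**What to change.** Keep 494 and make these changes in the Sample size calculation section:

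1. Check appendix 1, and state in the section the significance level, the formula, the role of the 1.5, and how the 20% was applied.
2. State that at 20% drop-out, power for 21/42 versus 28/42 is about 79%, naming the significance level and formula behind that figure. If appendix 1 shows a different level or formula, recompute before inserting it.
3. Only if appendix 1 confirms multiplication by 1.2, add that the allowance covers drop-out of about 17%, which corresponds to about 206 completers per group at 12 months (205.5 rounded up).

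The cost is a look at an existing appendix and one or two sentences. No extra participants are needed, and the stated power becomes slightly less favourable.

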**Data management and statistical analysis**

A data management plan is being developed using a tool from the Norwegian Centre for Research Data (NSD). UiO is responsible for the data stored in TSD. The de-identification code will be stored separately in TSD, and deleted in 2022. After this, the anonymous data will be kept in NSDs archives, for re-use purposes.

The data will be analysed in TSD, by multilevel models to address the dependency related to cluster trials. Summary tables with calculated averages (mean, median, and mode), will be created. The baseline knowledge scores will be calculated with data from the first survey. The doctoral research fellow will compute an overall score for each section (prevalence, cause/transmission, symptoms, treatment and prevention) at individual and village level, based on the answers to the questions. Then a comparison between intervention groups and between intervention and control groups will be made. Data from the follow-ups will also be analysed in TSD accordingly.

After data collection is completed the GPS data will be able to illustrate the use of the intervention, related to distance from household to Wi-Fi spot and frequency of use. In this planned illustration, no direct households will be identified, but rather summarize on village level the frequency of the use of the intervention.

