### **Main objectives in WP 2**

- Assess the effect of the digital health intervention, related to knowledge uptake and knowledge retention by assessing the knowledge score before and after the intervention, in both groups.
- To investigate if the intervention increase health literacy related to the intervention diseases among the clients that cannot read.

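### Does the analysis section need rewriting because it names no baseline term, no 42-item total and no primary time point?

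*Combined protocol and SAP*

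**What the plan says.** Under 'Data management and statistical analysis', the plan uses multilevel models to handle clustering. On baseline it states only that "The baseline knowledge scores will be calculated with data from the first survey". For the outcome scores, the task given to the PhD candidate is to "compute an overall score for each section (prevalence, cause/transmission, symptoms, treatment and prevention) at individual and village level". The group contrast is described in one sentence: "Then a comparison between intervention groups and between intervention and control groups will be made". On the later rounds the section adds no more than "Data from the follow-ups will also be analysed in TSD accordingly".

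Earlier sections state the purpose of that comparison. 'Main objectives in WP 2' assesses uptake and retention "by assessing the knowledge score before and after the intervention, in both groups". The sentence labelled as the hypotheses in the WP 2 section expects more correct answers "when comparing pre and post knowledge scores, also among clients that cannot read". The next paragraph says the study will measure an "increase in the number of correctly answered questions, from 21 out of 42, to 28 out of 42", and it places this gain "during the 12-months intervention in the intervention group compared to the control group". 'Sample size calculation' uses the same 21 and 28 of 42. 'Methods and study design' names both uptake and retention over the year as the main outcome.

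**The concern.** The intervention villages were chosen by convenience and there are two villages per group, so nothing in the allocation makes baseline knowledge equal. If the groups differ at the start, a follow-up-only comparison, a change contrast and a baseline-adjusted (ANCOVA) contrast can give three different answers. The analysis section commits to none of them. It lists five section scores but not the 42-item total behind the target, and it singles out no round.

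A reader could fear two things: that a difference between villages is reported as an effect, and that score, round and method are settled after the data are seen.

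**Working it through.** **1. The sections side by side**

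| Open item | What the analysis section says | What other sections say |
|---|---|---|
| Use of baseline | Baseline scores are calculated | Before and after scores in both groups (WP 2 objectives); an increase measured against control (WP 2 section) |
| Score | Five section scores | A count out of 42 (WP 2 section; sample size) |
| Round | Follow-ups analysed in the same way | A 12-month period (WP 2 section); uptake and retention (study design) |

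The first two items are answered in intent: compare the change in the 42-item count between groups. Only the algebraic form of the baseline term and the choice of round stay open.

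**2. The plan's own figure**

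Inputs: p1 = 21/42 = 0.500, p2 = 28/42 = 0.667, power 80%, 20% dropout and the clustering figure of 1.5, used as a design effect. A two-sided 5% level is assumed, because appendix 1 is not available.

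The pooled two-proportion formula is n = [1.96√(2p̄(1−p̄)) + 0.842√(p1(1−p1)+p2(1−p2))]² / (p2−p1)², with p̄ = 0.583. It gives 136.2, so 137 per group.

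- 137 × 1.5 = 205.5
- 205.5 × 1.2 = 246.6, so 247 per group
- 2 × 247 = 494, as in Table 2 (195 + 52 = 247 and 135 + 112 = 247)

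This formula has no baseline term and no time point, so it does not settle the analysis.

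**3. Size of the bias that was feared**

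The documents give no baseline gap; it may be zero. Assume a lasting gap of 1 item against the 7-item target, and a baseline to follow-up correlation r = 0.5.

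- Follow-up only: 1/7 = 14%
- ANCOVA leaves (1−r) of the gap: 0.5/7 = 7%
- Change contrast: 0%, if village trends are parallel

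The 14% belongs to an analysis that no section proposes.

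**4. Does the choice of method threaten power?**

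After 20% loss and the design effect, n = 247 × 0.8 / 1.5 = 131.7 per group. Relative to follow-up only, the variance is 2(1−r) for change and 1−r² for ANCOVA. At r = 0.3 these are 1.40 and 0.91. Put into the two-proportion formula, power is 64% for change, 79% for follow-up only and 82% for ANCOVA, which looks like a real cost of using change.

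That formula treats each person as one yes/no outcome. On the 42-item scale it implies an SD of 42 × √(0.5 × 0.5) = 21.0 items at 21/42. This is the largest SD possible at that mean, with half the people scoring 0 and half 42. For a mean score, the standard error of the change contrast is SD × √(2 × 1.40 / 131.7), and power is Φ(7/SE − 1.96):

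| Assumed SD (items) | SE | Power of the change contrast, r = 0.3 |
|---|---|---|
| 10 | 1.46 | 99.8% |
| 12 | 1.75 | 98% |
| 14 | 2.04 | 93% |
| 21 | 3.06 | 63% |

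The apparent loss of power comes from the yes/no formula. At SDs of 10 to 14, either method detects 7 items.

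**The case for a change.** The strongest opposing case is that intent is not specification. The multilevel models are introduced to deal with clustering, and such a model can be follow-up-only, change or baseline-adjusted. Five section scores at 3, 6 and 12 months allow 5 × 3 = 15 controlled contrasts. If each were tested at 5% and all were independent, the chance of at least one false positive would be 1 − 0.95^15 = 54%.

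It is true that the analysis section contains no model equation and names no primary round. The 54% is an upper illustration: scores from the same people are correlated, which lowers it, and the plan sets its numerical target on the total, not on the sections.

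Naming a round would also have a cost. The 12 months in the WP 2 section is a period, not a visit, and the main outcome covers both uptake and retention. Making 12 months primary would demote uptake, while an earlier round would demote retention.

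One wording discrepancy also stands. 'Recruitment and participants' speaks of five interviews for household members, but describes the immediate post-exposure round for group 1 only. Baseline plus three follow-ups makes four for controls. The controlled contrasts at 3, 6 and 12 months do not depend on that immediate round.

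**Conclusion.** No change to the plan is called for. The analysis section is brief and leaves out detail, but read with the WP 2 objectives and the 21-to-28 target it leads an analyst to a sound analysis: the 42-item count, before and after, intervention against control, in a multilevel model. Asking for more would mainly ask the sponsor to write down a choice between two defensible methods, and to pick one round at the expense of half of the stated main outcome.

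The 14% bias would arise only in a follow-up-only comparison, and only if a 1-item gap existed and persisted. The power argument against using change does not hold for a mean score with an SD of 10 to 14 items, where power is 99.8% to 93% at r = 0.3.

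This conclusion rests on assumed values for the SD, the correlation and the gap, none of which the documents give, and on a two-sided 5% level and the plan's own design effect of 1.5. With two villages per group, any baseline-accounted contrast still assumes that village trends are comparable. More detail in the analysis section would not remove that limit.

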**WP3 - Semi-structured interviews**

In order to get complimentary qualitative data, 8-10 semi-structured interviews with clients from the intervention villages will be conducted. The main aim is to get people to reveal their own perspectives related to the intervention.

The research question reads as follows: How is the intervention perceived and received among those who use it in the intervention villages?

Semi-structured interviews allow the doctoral research fellow to have an informal tone with the informants, and it adds meanings, values, feelings, personal experiences and points of view to the research. A checklist will be prepared to steer the conversations and make sure that no question remains unanswered or unclear. The interviews will be held with clients in the intervention villages, in English if possible, otherwise in Swahili with a translator. This is to provide in-depth information on how the intervention is perceived and received

among the people who actually use the intervention locally. It can also shed light on the possible effects of the intervention, raise specific issues, opportunities and problems, and provide a different view on the use of the health messages. The interviews can also work as a discussion arena and a strategy of validity.

The participants will be randomly picked from the same lists as in WP2. The semi-structured interviews will be recorded with the recording app from TSD, and transcribed thereafter. The records and transcription will be held separately from the de-identification code, both in the TSD. The de-identification code will be deleted two years after the overall project is finished. After this, the data will be kept anonymous in the NSD archives. When analysing and summarizing the interviews, a table will be made that excerpts the most important findings from the qualitative research, together with quotes from the interview.

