### **Main objectives in WP 3**

- Explore the reception and perception of the intervention among the users, by semi-structured interviews.

The doctoral research fellow will strive to present and review the findings from the research within the Sustainable Development Goals (SDGs), as over-arching framework. There are especially two goals of major importance related to this study: SDG 3 *Good health and well-being*, and SDG 9 *Industry, innovation and infrastructure*.

One of the targets in SDG 3, states that they are making a bold commitment to end the epidemics of (among others) HIV/AIDS and TB by 2030. Another target emphasizes to strengthen the capacity of all countries, in particular developing countries, for early warning, risk reduction and management of national and global health risks. Bridging the digital gap is an important task related to targets of SDG 9. They state among other targets: “*Significantly increase access to information and communications technology and strive to provide universal and affordable access to the Internet in least developed countries by 2020*”. The DigI project directly addresses this target through the aim of free access to information for all. The free access to information is also the catalyst for several other SDG goals (4, 8, 10 and 11).

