### **Recruitment and participants**

The research population is people living in the selected villages, the study units are individuals, but only people over 15-70 years old are eligible for participating in the study. This is a two-stage cluster where the intervention villages initially were sampled by stratification, and two-stage sampling frame will be undertaken at a ten-cell and household level. The number of households within the ten-cells will be selected by the size of the ten-cell, according to the Probability Proportional to Size. In the randomly chosen households, 3-4 household members will be interviewed all together five times. Ten-cell and household lists will be used for randomisation in both groups.

A baseline survey conducted in both groups will determine the knowledge with regard to the diseases in the groups before the intervention is implemented.

In group 1, the random selected sample of people, previously naïve to health messages delivered by the DigiI project, will be given the intervention physically, as they will be shown the digital health messages at the researchers/ enumerators tablets. This is to make sure that all the participants in group 1 will actually receive the intervention, in order for the analysis to be able to indicate the overall effect of the digital health messages. All the participants in group 1 will be informed that the intervention is available for all, at all times, in the local Wi-Fi spot, however, we cannot be certain that the participants will use the intervention more than the first exposure by the enumerators.

Group 1 will, immediately after the exposure to the digital health messages, be asked the same questions as in the baseline questionnaire. 3 months, 6 months and 12 months after first exposure to the intervention, the questions will be repeated to the same participants.

Inclusion criteria:

- Living in the selected household (15-70 years), at least for the past six months, and at least planning to not move the next 12 months.
- Must be capable and willing to sign written informed consent and thumb-print for illiterate participants

Exclusion criteria

- Planning to be out of the village for more than 6 weeks in the next 12 months
- Those above 71 or under 15
- Not capable of signing consent letter (very sick)

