A personal device, the tablet, containing:	Household lists, containing:

 
• A digital questionnaire (KoboCollect) with:               
 
1. DOI, Age segment, sex
 
2. 14 knowledge questions on HIV / AIDS
 
3. 11 knowledge questions on TB
 
4. 17 knowledge questions on TSCT
 
5. 5 questions on digital literacy
 
6. 6 questions on general health literacy
 
 
 
• Digital health messages.
 
	
 
• The personal identification key (household lists) with:               
 
1. DOI
 
2. Name
 
3. Sex
 
4. Age
 
5. Village
 
6. Mobile number
 
7. GPS-coordinates
 
 
 

Table 1

The reason for asking the participants for their names, mobile number and GPS is to be able to re-locate the participants in the follow-up surveys. In the follow-ups, the research staff will carry lists with GPS-coordinates,

together with names and DOIs. When entering the data from the follow-ups, the enumerators will only have to identify the participants according to the list, and use the DOI when collecting data.

In the follow-ups, the participants will be asked if they have used the intervention, at the local Wi-Fi spot, and if yes, how many times in the previous (three/six) months. This will provide information on the actual use of the intervention.

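### WP3 asks about people who actually use the platform but picks its 8-10 interviewees without regard to use or village, so it may include few or no Wi-Fi users and can miss Izazi

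*Combined protocol and SAP*

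**What the plan says.** - **The question.** The WP3 section asks "How is the intervention perceived and received among those who use it in the intervention villages" and says the interviews will inform on reception "among the people who actually use the intervention locally". Main objectives in WP 3 reads "Explore the reception and perception of the intervention among the users, by semi-structured interviews".
- **The selection.** In the WP3 section, "8-10 semi-structured interviews with clients from the intervention villages will be conducted", and "The participants will be randomly picked from the same lists as in WP2". That section gives no screening, stratification or replacement by use or by village.
- **How use is recorded.** Under Study tools, at the follow-ups "the participants will be asked if they have used the intervention, at the local Wi-Fi spot", and how often. The protocol treats the answer as its information on actual use. Data management and statistical analysis plans to relate that use to distance from the Wi-Fi spot. Neither section is linked to WP3.
- **Exposure.** Under Recruitment and participants, enumerators show the messages to each group 1 participant on a tablet: "This is to make sure that all the participants in group 1 will actually receive the intervention". The same paragraph adds that "we cannot be certain that the participants will use the intervention more than the first exposure by the enumerators".
- **Villages and timing.** The Project summary says interviewees come from each intervention village and schedules the interviews with the 3-, 6- and 12-month follow-ups. Table 2 allocates 195 participants to Migoli and 52 to Izazi.

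No expected rate of Wi-Fi spot use is given anywhere.

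**The concern.** The question and the selection rule refer to different groups. The question concerns people who use the platform where they live. The rule draws from everyone on the list, so it returns such people only in proportion to their share of the list.

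That share could be small. The Introduction gives the Wi-Fi a reach of 50 m, Recruitment and participants describes dispersed populations, and the plan itself doubts whether participants will return after the first showing. With only 8-10 interviews, randomness offers little protection.

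At stake is the part of WP3 that only self-directed users can supply: how the platform works for people who sought it out. Understanding use belongs to the project's primary objective, and one planned article is about experience with implementation. If few interviewees went to the Wi-Fi spot, that article would mainly describe how a supervised tablet viewing was received.

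The village split matters too. Methods and study design says Izazi has no internet connection while Migoli recently gained 3G, so an all-Migoli set would lose one of the two settings.

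**Working it through.** **1. The list being sampled.** The 8-10 interviews have no stated derivation, but the list they come from does. Comparing 21/42 = 50% with 28/42 = 66.7% at 80% power and two-sided 5% (the level is my assumption, as none is stated) needs 137 per group. Then 137 × 1.5 = 205.5; 205.5 × 1.2 = 246.6, rounded up to 247; 247 × 2 = 494. This matches Table 2, where 195 + 52 = 247 and 135 + 112 = 247. WP3 is confined to the intervention villages, so the list is 247 people.

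**2. Chance of reaching Wi-Fi users.** Let u be the share of the list that has used the Wi-Fi spot (assumed, since no rate is given) and n the number of interviews. The expected number of users is n·u. The chance of none is (1 − u)^n. The chance of at most two is the binomial sum over 0, 1 and 2.

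| u | Expected users, n = 8 / 10 | No user, n = 8 / 10 | At most two, n = 8 / 10 |
|---|---|---|---|
| 5% | 0.4 / 0.5 | 66% / 60% | 99% / 99% |
| 10% | 0.8 / 1.0 | 43% / 35% | 96% / 93% |
| 20% | 1.6 / 2.0 | 17% / 11% | 80% / 68% |
| 30% | 2.4 / 3.0 | 6% / 3% | 55% / 38% |
| 50% | 4.0 / 5.0 | 0.4% / 0.1% | 14% / 5% |

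Sampling without replacement from 247 changes these by about one point (at u = 10%, no user becomes 42.0% for n = 8 and 33.7% for n = 10).

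**3. Chance of missing Izazi.** No use rate is needed here. For n = 8 the chance that all interviewees come from Migoli is (195/247) × (194/246) × … × (188/240) = 0.146. For n = 10 the product runs on to 186/238 and equals 0.089. The expected number from Izazi is 8 × 52/247 = 1.7 or 10 × 52/247 = 2.1.

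**4. Are there enough users to select from?** At 5% use, 247 × 0.05 ≈ 12, enough to fill 8-10 places. At 2% it is 247 × 0.02 ≈ 5, which is not. In Izazi alone, 5% and 10% give 52 × 0.05 = 2.6 and 52 × 0.10 = 5.2.

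**The case against.** The strongest reply is that everyone in group 1 is a user. The Project summary equates the interviewed clients with users, and the Introduction describes WP3 as interviews with intervention-group clients. The section on developing the intervention says that it consists of the messages, not the hotspot. The sentence doubting use beyond the first exposure can be read as counting that exposure as use. On this reading the chance of interviewing no user is zero at every rate. WP3 also has a broader aim of hearing people's own perspectives, and those who watched once and never returned can speak to barriers. Interviewing only repeat visitors would favour the motivated.

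Much of this stands. A reader might infer that WP3 cannot answer its question, or that its interviewees will mostly be non-users. The documents support neither: every group 1 participant has seen the messages, and no use rate is stated. The reply is also a good reason to keep some once-exposed participants. Nor does the fact that the WP2 lists cover four villages mean control participants could be drawn, because WP3 restricts the interviews to the intervention villages.

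What remains is that the protocol uses the word in two senses and never says which governs selection. If the supervised showing counted as use, the follow-up question about the Wi-Fi spot would not be needed to learn actual use, and WP3's emphasis on actual, local use would add nothing. The village point does not depend on this. The Project summary states the intention, but the selection rule does not secure it.

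**Conclusion.** The concern holds as a gap between WP3's question and its selection rule, worth closing before the interviews are drawn. WP3 can describe how the messages were received, but the rule does not assure that it hears from people who used the platform themselves. At 10% use, a set with no such person has a chance of roughly two in five with 8 interviews and one in three with 10. At 20% use no user at all is less likely, but two or fewer is still the usual result. At 50% or more, having none is negligible. Where the study falls in this range is unknown until follow-up. The risk of omitting Izazi rests on the plan's own allocation.

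The figures assume that use means Wi-Fi spot use, that the lists are the enrolled group 1 participants, and that each has the same chance of selection. If the lists were instead the household sampling lists, even the single showing would not be guaranteed. Only the qualitative component is affected; the WP2 effect estimate is not.

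**What to change.** Replace the selection sentence in WP3 with a stratified draw:

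- State that the list is the enrolled group 1 participants, and define a user as someone who reports Wi-Fi spot use at the 3- or 6-month survey.
- Draw at random within strata of village (Migoli, Izazi) and reported use, with places reserved for each village.
- Give most of the 8-10 places to reported users, taking all of them if there are too few.
- Keep a few participants who saw the messages only at the enumerator's showing, and report the two groups separately.

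The cost is small. The use question is already in the follow-up questionnaire. Holding the interviews after the first follow-up fits the schedule in the Project summary. The one new step is data handling: use answers are stored by participant code, apart from names, so selection needs a link through the identification key. The protocol does not describe that purpose, so the data management text should cover it.
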